Appendix IV. Study Schedule

Appendix I	screeni ng					Thera	ару				End of	Follo w-up
Cycle No.				1				2	3	n	Stud	visit
Duration				280			2	8d	28 d	28 d	y visit	
Relative day within cycle	(-)28	1	2	8	1 5	2	1	1 5	1	1		
Baseline Procedure												
Informed Consent	Х											
Inclusion/Exclusion	Х											
Demography, Relevant medical history, current medical conditions including AML- specific history	Х											
Evaluation of FLT3- D835, FLT3-ITD, and other mutational status	Х											
Routine Examination												
Prior/Concomitant medications, significant non- drug therapies	Х	Х					Х		Х	Х	Х	Х
Physical examination ^a	Х	Х					Х			Х	Х	Х
EKG ^b	X	Χ										
Vitals, ECOG Performance Status, Weight	Х	Χ	Х	Х	Х	Х	Х	Х	Х	Х	Х	Х
AEs and SAEs	Х	Χ	Χ	Χ	Χ	Χ	Х	Χ	Х	Х	Х	Х
Laboratory tests												
Hematology ^c	Х	X X		X X	Х	Х	Х	Х	Х	Х	Х	Х
Serum Chemistries ^d	Х	X		X X	Х	Х	Х	Х	Х	Х	Х	Х
HIV, HepB/C	Х											
Urine or serum Pregnancy test	Х										Х	
Peripheral blood for PK analysis ^e		Х	Х		Х		Х		Х			
Peripheral blood for correlative		Х	Х		Χ		Х		Х			

analysis [†]								
Disease assessment								
Bone marrow aspirations (x2) ^g	Х	Χ			Χ	Х	Х	

^a Physical exam can be done within ±4 days of start of cycle 1 and cycle 2 then every 2 cycles

^{c,d} CBC includes platelet count, differential (differential may be omitted if WBC is $<0.5 \times 10^9/L$) and Chemistry panel including creatinie, AST, ALT, and total bilirubin to be drawn twice weekly (at least 24 hours apart) for the first two weeks of cycle 1, once weekly (\pm 3 days) for the second two weeks of cycle 1, bi-weekly (\pm 4 days) for the second cycle and once a month thereof from cycle 3 until cycle 12 (\pm 14 days).

Labs obtained with the local physician can be used for monitoring; PI or designee must review and sign source documents within 24 hours of performance of lab at local physician's office unless performed on a Friday in which case review on the following Monday is acceptable. It is encouraged that labs be performed on Monday thru Thursday.

At the time of any dose escalation, labs should be drawn twice per week for at least one week.

^{e,f} Peripheral blood for translational research and correlative analysis including Pharmacokinetics Assay and Plasma Inhibitory Assay will be obtained at multiple time points on Day 1 of Cycle 1, the 24 hour drug level would be obtained on Day 2 of Cycle 1. Samples will also be obtained at multiple time points on Day 15 of Cycle 1, and Day 1 of Cycle 2 and Cycle 3. Additional samples may be drawn at the discretion of the investigator.

^g Two bone marrow aspirations will be collected on day 1 (+4 days) of the second cycle, day 1 (±4 days) of the third cycle, then every 3 cycles (+/- 1 cycle) for as long as CR is maintained. At loss of CR, bone-marrow biopsy will be performed only as clinically indicated to exclude toxicity issues.

^b EKG measurements to be obtained at 1 hour (± 30 mins) post first or second dose, in accordance to the visit. If new drugs with known effect on QTc are to be co-administered with crenolanib, EKGs including a baseline prior to start of the new agent and 2-3 days after starting patient on combination of drugs is recommended. Weekly EKG x3 is also recommended for follow up and as needed for assessment based on patient's clinical condition. EKG can then be resumed per study schedule

Appendix V. Clinical Laboratory Tests

Hematology^a Clinical Chemistry^b

Hemoglobin Serum Concentrations of:

Hematocrit Sodium
Erythrocyte count (RBC) Potassium
Leukocytes (WBC) Total bilirubin
Neutrophils, segmented Direct bilirubin
Lymphocytes Indirect bilirubin

Monocytes

Eosinophils Alanine aminotransaminase (ALT/SGPT)
Basophils Aspartate aminotransferase (AST/SGOT)

Platelets

Blood urea nitrogen (BUN)

Creatinine Phosphorus Calcium

Glucose, random

Albumin

Lactate dehydrogenase

Pregnancy Test (serum or urine; females only) a,c,d

Abbreviations: RBC = red blood cells, WBC = white blood cells.

- a Can be performed by local lab
- b Local Lab results may be used for enrollment or dosing decisions
- c Required for women of childbearing potential. Women are considered not of childbearing potential if they are surgically sterile or are postmenopausal. Patients may be entered and enrolled on the basis of a local serum or urine pregnancy test
- d Repeat test as clinically indicated

Protocol: ARO-004

e Repeat test on Day 1 of each cycle of therapy.

Note: Patients may be enrolled on the basis of local chemistries.

Investigators must document their review of each lab report.

Appendix VI. Common Terminology Criteria for Adverse Events (CTCAE); Version 4.03

		Investigations			
			Grade		
Adverse Event	1	2	3	4	5
Platelet count decreased	<lln -="" -<br="" 75,000="" <lln="" mm3;="">75.0 x 10e9 /L</lln>	<75,000 - 50,000/mm3; <75.0 - 50.0 x 10e9 /L	<50,000 - 25,000/mm3; <50.0 - 25.0 x 10e9 /L	<25,000/mm3; <25.0 x 10e9 /L	
Definition: A finding based on lat	Definition: A finding based on laboratory test results that indicate a decrease in number of platelets in a blood specimen	decrease in number of platelets in	a blood specimen.		
Neutrophil count decreased	<pre><lln -="" 1.5="" 10e9="" 1500="" <lln="" l<="" mm3;="" pre="" x=""></lln></pre>	<pre><lln -="" 1.5="" 1500="" <lln="" mm3;="" td="" x<=""><1000 - 500/mm3; <1.0 - 0.5 x 10e9 /L	<500/mm3; <0.5 × 10e9 /L		</lln></pre>	<1000 - 500/mm3; <1.0 - 0.5 x 10e9 /L	<500/mm3; <0.5 × 10e9 /L	
Definition: A finding based on lat	Definition: A finding based on laboratory test results that indicate a decrease in number of neutrophils in a blood specimen.	decrease in number of neutrophils	in a blood specimen.		
Anorexia	Loss of appetite without alteration in eating habits	Oral intake altered without significant weight loss or malnutrition; oral nutritional supplements indicated	Associated with significant weight loss or malnutrition (e.g., inadequate oral caloric and/or fluid intake); tube feeding or TPN indicated	Life-threatening consequences; urgent intervention indicated	Death
Definition: A disorder characterized by a loss of appetite.	red by a loss of appetite.				
Diarrhea Definition: A disorder characteriz	Diarrhea Increase of <4 stools per day Increase o over baseline; mild increase in over basel ostomy output compared to increase ir baseline compared to compared baseline compared by frequent and watery bowel movements.	Increase of 4 - 6 stools per day over baseline; moderate increase in ostomy output compared to baseline	Increase of >=7 stools per day over baseline; incontinence; hospitalization indicated; severe increase in ostomy output compared to baseline; limiting self care ADL	Life-threatening consequences; urgent intervention indicated	Death
	(1000)				
Fatigue	Fatigue relieved by rest	Fatigue not relieved by rest; limiting instrumental ADL	Fatigue not relieved by rest, limiting self care ADL		
Definition: A disorder characteriz	Definition: A disorder characterized by a state of generalized weakness with a pronounced inability to summon sufficient energy to accomplish daily activities.	less with a pronounced inability to	summon sufficient energy to acco	mplish daily activities.	
Nausea	Loss of appetite without alteration in eating habits	Oral intake decreased without significant weight loss, dehydration or malnutrition	Inadequate oral caloric or fluid intake; tube feeding, TPN, or hospitalization indicated		
Definition: A disorder characteriz	Definition: A disorder characterized by a queasy sensation and/or the urge to vomit.	ne urge to vomit.			
Vomiting	1 - 2 episodes (separated by 5 minutes) in 24 hrs	3 - 5 episodes (separated by 5 minutes) in 24 hrs	>=6 episodes (separated by 5 minutes) in 24 hrs; tube feeding, TPN or hospitalization indicated	Life-threatening consequences; urgent intervention indicated	Death
Definition: A disorder characteriz	Definition: A disorder characterized by the reflexive act of ejecting the contents of the stomach through the mouth	he contents of the stomach through	h the mouth.		
Alanine aminotransferase increased	>ULN - 3.0 × ULN	>3.0 - 5.0 × ULN	>5.0 - 20.0 × ULN	>20.0 × ULN	
Definition: A finding based on lak	Definition: A finding based on laboratory test results that indicate an increase in the level of alanine aminotransferase (ALT or SGPT) in the blood specimen.	increase in the level of alanine ar	ninotransferase (ALT or SGPT) in	the blood specimen.	
Aspartate aminotransferase increased	>ULN - 3.0 × ULN	>3.0 - 5.0 × ULN	>5.0 - 20.0 × ULN	>20.0 × ULN	
Definition: A finding based on lak	Definition: A finding based on laboratory test results that indicate an increase in the level of aspartate aminofransferase (AST or SGOT) in a blood specimen	increase in the level of aspartate	aminotransferase (AST or SGOT)	in a blood specimen.	
Blood bilirubin increased	>ULN - 1.5 × ULN	>1.5 - 3.0 × ULN	>3.0 - 10.0 × ULN	>10.0 × ULN	
Definition: A finding based on lak	Definition: A finding based on laboratory test results that indicate an abnormally high level of bilirubin in the blood. Excess bilirubin is associated with jaundice	abnormally high level of bilirubin	In the blood, Excess bilirubin is as	sociated with jaundice.	

Appendix VII. Definition of a Serious Adverse Event (SAE)

Life threatening: "Life threatening" means that the patient was at immediate risk of death from the adverse event as it occurred or it is suspected that use or continued use of the product would result in the patient's death. "Life threatening" does not mean that had an adverse event occurred in a more severe form it might have caused death (i.e., hepatitis that resolved without hepatic failure).

Hospitalization: Outpatient treatment in an emergency room is not in itself a serious adverse event, although the reasons for it may be (e.g., bronchospasm, laryngeal edema). Hospital admissions and/or surgical operations planned before or during a study are not considered adverse events if the illness or disease existed before the patient was enrolled on the study, provided that it did not deteriorate in an unexpected way during the study.

Important medical event or medical intervention: Medical and scientific judgment should be exercised in deciding whether a case is serious in a situation where important medical events may not be immediately life threatening or result in death, hospitalization, disability or incapacity but may jeopardize the patient or may require medical intervention to prevent one or more outcomes listed in the definition of serious. These should usually be considered as serious.

Examples of such events are:

- · Angioedema not severe enough to require intubation but requiring intravenous hydrocortisone treatment
- Hepatotoxicity caused by paracetamol (acetaminophen) overdose requiring treatment with N-acetylcysteine
- · Intensive treatment in an emergency room or at home for allergic bronchospasm
- Blood dyscrasias (e.g., neutropenia or anemia requiring blood transfusion, etc.) or convulsions that do not result in hospitalization
- Development of drug dependency or drug abuse

Disease progression: Any events or hospitalizations that are unequivocally due to progression of disease must not be reported as serious adverse events.

The following factors should be considered when deciding if there is a "reasonable possibility" that an adverse event may have been caused by the investigational product.

- Time course of events and exposure to suspect drug: Has the patient actually received the suspect drug? Did the adverse event occur in a reasonable temporal relationship to the administration of suspect drug?
- Consistency with known drug profile: Was the adverse event consistent with the previous knowledge of the suspect drug (pharmacology and toxicology) or drugs of the same pharmacological class? OR could the adverse event be anticipated from its pharmacological properties?
- De-challenge experience: Did the adverse event resolve or improve on stopping or reducing the dose of the suspect drug?

- No alternative cause: The adverse event cannot be reasonably explained by another etiology, such as the underlying disease, other drugs, other host, or environmental factors.
- Re-challenge experience: Did the adverse event reoccur if the suspected drug was reintroduced after having been stopped? Laboratory tests: Has a specific laboratory investigation confirmed the relationship?

A "reasonable possibility" could be considered to exist for an adverse event when 1 or more of these factors exist.

In contrast, there would not be a "reasonable possibility" of causality if none of the above criteria apply, or if there is evidence of exposure and a reasonable time course, but any de-challenge (if performed) is negative or ambiguous, or there is another more likely cause of the adverse event.

In difficult cases, other factors could be considered such as the following:

- Is this a recognized feature of overdose of the drug?
- Is there a known mechanism?

Protocol: ARO-004

Ambiguous cases should be considered as having a "reasonable possibility" of causal relationship, unless additional evidence becomes available to refute this.

If true progression is determined by subsequent imaging, then the date of progression returns to the earlier date with increasing mass.

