10.3.9 Safety Analyses

All patients will be evaluable for safety. Adverse events that occur after a patient is entered (signs informed consent), but before the patient receives study drug, will not be recorded on the CRF unless the investigator believes that the events may have been caused by a protocol procedure. Safety analyses will include summaries of the incidence of adverse events by maximum CTCAE grade (version 4.03; NCI 2010) that occur during the study treatment period or within 30 days of the last dose of study treatment, regardless of causality or relatedness to study drug. The safety-related outcomes that will be summarized include:

- Adverse events,
- TEAEs,
- SAEs,
- Deaths.
- Discontinuations due to adverse events,
- Extent of exposure to study drug treatment,
- Hospitalizations,
- Use of key concomitant medications (for example, antipruritus medication).

Analyses for data with discrete dates (for example, deaths and concomitant medications) will be performed through 30 days after the patient has been discontinued from study treatment. Adverse events will also be analyzed in this time frame. After 30-day post-discontinuation follow-up, only those SAEs that are thought to be related to study treatment or protocol procedure should be reported immediately to AROG or its designee. For these events, the patient must be followed until the event has resolved or stabilized.

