11.1.2 Serious Adverse Event Definition

ICH Guideline E6 defines serious adverse events as those events which meets any of the following criteria (Appendix VII):

- Fatal
- Immediately life-threatening
- Results in inpatient hospitalization or prolongation of existing hospitalization
- Results in persistent or significant disability/incapacity
- Results in a congenital anomaly/birth defect

Note: Medical and scientific judgment should be exercised in deciding whether expedited reporting is appropriate in other situations; for example, important medical events may not be immediately life-threatening or result in death or hospitalization, but may jeopardize the patient or may require intervention to prevent one of the outcomes listed in the definition above. Any adverse event is considered a serious adverse event if it is associated with clinical signs or symptoms judged by the investigator to have a significant clinical impact.

Hospitalizations that do not meet these criteria are:

- surgery or procedure planned prior to entry into the trial
- social reason in the absence of an adverse event

Study-specific clinical outcomes of death from PD should be reported as an SAE only if the investigator deems them related to use of the study drug.

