11.1.6 Serious Adverse Event Reporting

Table 11.1 outlines adverse event and serious adverse event (SAE) assessment and follow-up guidelines.

Table 11.1. Adverse Events/Serious Adverse Events Assessment Guide

Time	After ICD/Before Drug	During Therapy	30-day Post- discontinuation follow-up period	Long-term follow-up period
Events to collect	AE/SAEs	New/ongoing AE/SAEs Regardless of relatedness to study treatment or procedures		New/ongoing SAEs
	Related to procedures			Related to study treatment or procedures

Serious adverse event collection begins after the patient has signed informed consent and has received a tablet or more of study drug. If a patient experiences an SAE after signing informed consent, but prior to receiving study drug, the event will NOT be collected unless the investigator feels the event may have been caused by a protocol procedure.

Study site personnel must alert AROG or its designee of any serious adverse event (SAE) within 24 hours of investigator awareness of the event via a sponsor-approved method. Alerts issued via telephone are to be immediately followed with official notification on study-specific SAE forms. All cases are recorded on the CRF and copy of an SAE report is provided to AROG by the site.

Important medical events that may not result in death, be life-threatening, or require hospitalization may be considered serious adverse drug events when, based upon appropriate medical judgment, they may jeopardize the patient or subject and may require medical or surgical intervention to prevent one of the outcomes listed in this definition.

Study-specific clinical outcomes of death from PD should be reported as an SAE only if the investigator deems them related to use of the study drug.

Any event deemed serious within the 30-day post discontinuation follow-up period, regardless of relatedness to study drug or protocol procedure, must be reported immediately to AROG or its designee.

AROG or its designee will be alerted to SAEs occurring after a patient's 30-day post discontinuation follow-up only if the investigator believes that the event may have been caused by the study drug.

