SAEs occurring after a patient has taken the last dose of study drug will be collected for 30 days after the last dose of study drug, regardless of the investigator's opinion of causation. Thereafter, serious adverse events are not required to be reported unless the investigator feels the events were related to either study drug or a protocol procedure.

All serious adverse events (SAE) will be reported to the study coordinator within 24 hours of the investigational staff's knowledge. This includes any event that occurs during the participation of the trial regardless of associated participation, severity or relationship.

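### Appendix VII bars SAE reports for non-fatal progression events that Sections 11.1.2, 11.1.6 and 11.1.7 require, so the SAE count depends on which rule a site follows

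*Combined protocol and SAP*

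**What the plan says.** **Appendix VII**, in its paragraph on disease progression, gives a prohibition: "Any events or hospitalizations that are unequivocally due to progression of disease must not be reported as serious adverse events".

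**Section 11.1.2** includes this among the criteria for a serious event: "Results in inpatient hospitalization or prolongation of existing hospitalization". The admissions it excludes are procedures planned before trial entry and social admissions without an adverse event.

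**Section 11.1.6** sets the reporting duty. Table 11.1 collects AEs and SAEs during therapy whether or not they are related. For the period after discontinuation the text says: "Any event deemed serious within the 30-day post discontinuation follow-up period, regardless of relatedness to study drug or protocol procedure, must be reported immediately". The section closes with "All serious adverse events (SAE) will be reported to the study coordinator within 24 hours of the investigational staff's knowledge", and adds: "This includes any event that occurs during the participation of the trial regardless of associated participation, severity or relationship".

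**The body's own exception** concerns death alone. Section 11.1.6 says that "death from PD should be reported as an SAE only if the investigator deems them related to use of the study drug", and Sections 11.1.2 and 11.1.7 repeat this. The list of SAE outcomes in Section 11.1.7 marks an exception against death and against no other outcome.

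**Section 11.1.5** says that events leading to death from progression are not sent to the sponsor as AEs on the case report form unless the drug may have caused them. It also says that they form part of the safety and efficacy analyses.

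**Section 10.3.9** summarises AE incidence by maximum grade "regardless of causality or relatedness to study drug". It lists SAEs, deaths and hospitalizations as separate outcomes.

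**The concern.** A site that admits a patient for plainly progressive leukaemia finds two opposite instructions in one protocol. Some sites may file an SAE and others may not, and the pooled SAE summary would then mix two definitions.

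This matters more here than in a randomised trial. There is no comparator in which the same inconsistency would occur, so the SAE incidence is read as an absolute figure. Safety and tolerability is the first secondary objective listed in Section 1.2, and the planned number is 14 evaluable patients, so a few differently classified events would show in the reported percentage.

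**Working it through.** The plan states no figure to reproduce. The check is to take each type of event and ask what each text tells the site to do.

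| Event | Body (11.1.2, 11.1.6, 11.1.7) | Appendix VII | Result |
|---|---|---|---|
| Non-fatal event or admission unequivocally due to progression, on therapy or within 30 days after | Report as SAE if serious | Do not report as SAE | **Conflict** |
| Death from progression, not deemed drug-related | Not an SAE | Not an SAE | Agree; only the broad closing sentence of 11.1.6 clashes |
| Death from progression, deemed drug-related | SAE | Not barred, since the cause is then not unequivocally progression | Agree |
| Serious event of uncertain cause | Report as SAE | Not barred; ambiguous cases are treated as possibly drug-caused | Agree |
| Serious event before first dose, not procedure-related | Not collected ("the event will NOT be collected unless the investigator feels the event may have been caused by a protocol procedure") | Silent | Consistent across 10.3.9, 11.1.6 and 11.1.7; the closing sentence of 11.1.6 is loose |

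The conflict is confined to the first row. It is a true conflict because Section 11.1.4 defines a not-related event as one due to the underlying disease or to other unrelated circumstances. A duty to report regardless of relationship therefore includes events caused by the leukaemia itself.

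**Link to Section 10.3.9.** The SAE summary depends directly on the first row. The hospitalization summary does so only if it is drawn from SAE forms, and the protocol does not name its source. The AE summary is not blocked: Appendix VII limits what is reported as an SAE, and Section 11.1.1 puts all AEs on the AE form whether related or not. The one gap in AE data comes from Section 11.1.5, which removes events leading to death from progression from that form and names no other source for the analyses that are to include them.

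**Size.** Inputs: 14 planned evaluable patients (synopsis) and k patients whose only serious event is a non-fatal one due to progression. The documents do not give k. The difference in SAE incidence between the two rules is k/14:

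- k = 1: 1/14 = 7.1 percentage points
- k = 2: 2/14 = 14.3 percentage points
- k = 3: 3/14 = 21.4 percentage points

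These values of k are illustrations. The shift is smaller if the safety denominator exceeds 14, which is possible: under Section 7.1, patients with less than 28 days of induction treatment are replaced for efficacy, but all patients are assessed for toxicity.

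**The case against.** The best defence is that Appendix VII is headed as the definition of an SAE. On that reading, progression events are removed before the reporting duty in Section 11.1.6 applies. This softens the conflict but does not settle it. Sections 11.1.2 and 11.1.7 both cite Appendix VII and still state the hospitalization criterion without its exclusion, Section 11.1.7 marks an exception for death alone, and no text says which prevails.

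A second defence is that the closing paragraph of Section 11.1.6 concerns notice to the study coordinator, not to the sponsor. That is true of the paragraph. But the 30-day rule in the same section requires notice to the sponsor or its designee regardless of relatedness, so the conflict remains.

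Three parts of the case on the other side stand in full and limit the point:

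- A reader might infer that the body makes every event reportable. It does not: the exception for death from progression is stated in three sections.
- A reader might infer that the all-causality summaries cannot be produced. They can, because events not reported as SAEs are still recorded as AEs, apart from the gap in Section 11.1.5.
- A reader might infer that drug toxicity, such as liver failure, would be screened out before the sponsor sees it. The text does not direct that. The bar covers only unequivocal progression, and Appendix VII treats ambiguous cases as possibly drug-caused. The liver-failure death described in Section 5.5.4 was classified as possibly related although hepatic progression had not been excluded.

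**Conclusion.** The inconsistency is real but narrow. For non-fatal events and admissions unequivocally due to progression, Appendix VII forbids an SAE report that Sections 11.1.2, 11.1.6 and 11.1.7 require. The SAE count under Section 10.3.9 therefore depends on site practice. Section 11.1.5 adds a smaller gap, because it assigns events to the safety analyses without saying where their data come from.

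The effect is 7.1 percentage points of SAE incidence per patient classified differently, assuming a denominator of 14 and that the patient has no other serious event. The total cannot be computed, since the documents give no share of serious events due to progression, and no multiplier on the SAE count can be supported. The pre-dose wording needs tidying but is not a second contradiction. This is a low-severity matter of wording that is cheap to correct.

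**What to change.** Reconcile Sections 11.1.2, 11.1.5, 11.1.6, 11.1.7 and Appendix VII into one rule applied at all sites.

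1. **Collection.** A workable rule is to record every serious event from first dose to 30 days after last dose, with a flag for events due to progression, and to report SAE totals with and without flagged events. Excluding progression events everywhere would also remove the conflict, but only one total could then be given.
2. **Deaths from progression.** Say explicitly how the rule treats the existing exception. Either such deaths are recorded with the flag and the exception is removed from Sections 11.1.2, 11.1.6 and 11.1.7, or the exception stays and applies identically throughout.
3. **Section 11.1.5.** Name the form that supplies events leading to death from progression to the safety analyses.
4. **Definition.** State what counts as progression for the flag. Section 9.1 lists response categories and gives no criteria for progression.
5. **Pre-dose events.** Align the closing sentence of Section 11.1.6 with the pre-dose rule in Sections 10.3.9, 11.1.6 and 11.1.7.

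The cost is revised wording, one field on the case report form, and some additional SAE forms for sites to complete.
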